9.3 Definition of Populations

Intent-to-treat population for the primary outcome is synonymous to those getting baseline and three-month biopsies, whether or not they adhere to the treatment. Every effort will be made to bring back participants for their three month (post-treatment) biopsy visit, regardless of their levels of adherence. Intent-to-treat for serial measurements will include those with at least one of their follow-up visits. As above, we shall make every effort to get all follow-up visits completed, regardless of adherence.

The per protocol (PP) population will consist of all patients in the ITT population who are not major protocol violators. Specifically, PP population will consist of individuals who did not take any prohibited therapies during the trial, had $\geq 90\%$ adherence with prescribed regimen based on pill counts, and completed all baseline and post-treatment assessments.

The gold standard for clinical trials is by intent-to-treat. An analysis of the prognostic significance of actual dose consumed over the active period has value since it will allow for further analysis of dose effects. This will be a secondary analysis, and will allow for determination of whether higher consumption while on active medication results in greater changes to outcome variables. For this study, a completer analysis will be performed on the target population of older adults (age \geq 65 years).

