4.2 Exclusion Criteria

All candidates meeting any of the exclusion criteria listed below at baseline will be disqualified from study participation.

- Non-English speaking individual.
- Failure to provide informed consent;
- Allergy/sensitivity to grapes or Japanese knotweed;
- Current dietary supplementation of grape seed extract or ginko biloba;
- Consumption of ≥ 8 oz. of red wine/dealcoholized red wine/red or purple grape juice more than once weekly;
- Consumption of any dietary supplements containing resveratrol, quercetin, or *P. cuspidatum* in the previous 90 days;
- Active treatment for cancer, stroke (< 6 months), peripheral vascular disease, coronary artery disease, myocardial infarction (< 6 months), congestive heart failure (stage III or IV), valvular heart disease, major psychiatric disease, severe anemia (blood levels of Hemoglobin < 8 g/dl), bleeding disorders or other blood disorders, liver or renal disease, diabetes, severe osteoarthritis, blindness or deafness, fracture in upper or lower extremity (< 6 months), upper or lower extremity amputation, or Parkinson's disease;

- Cognitive impairment (i.e. Mini Mental Status Exam ≤ 23);
- History of significant head injury that currently interferes with functioning;
- Severe physical limitations (i.e., < 4 on the Short Physical Performance Battery);
- Hard exercise (i.e. running, bicycling, etc.) ≥ 30 min on five or more days per week;
- Excessive alcohol use (> 2 drinks/day) or alcohol abuse (> 5 drinks/day for males, or > 4 drinks/day for females);
- History of substance abuse within the past six months;
- Mood disorder (i.e. Center for Epidemiological Studies Depression (CES-D) ≥ 16);
- History of tobacco use within the past three years;
- Resting heart rate > 120 bpm at screening visit;
- Systolic blood pressure > 160 mm Hg at screening visit;
- Diastolic blood pressure > 90 mm Hg at screening visit;
- Fasting glucose ≥ 126 mg/dL at screening visit;
- Abnormalities in blood chemistry parameters, defined by blood chemistry marker outside of healthy range) as determined by study physician;
- Current use of
 - o anabolic treatments (e.g. growth hormone or testosterone),
 - o anticholinesterase inhibitor (e.g. Aricept),
 - o hormone replacement (e.g. Estrogen),
 - o anticoagulant therapies (note: aspirin -anti-platelet use (≤ 81 mg/day) is permitted) or
 - o use of anti-inflammatory medications more than 3 times per week

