5.3.3 Prohibited Interventions

- Active treatment for cancer, stroke, peripheral vascular disease, coronary artery disease, myocardial infarction, congestive heart failure (stage III or IV), valvular heart disease, major psychiatric disease, severe anemia, liver or renal disease, diabetes, severe osteoarthritis, blindness or deafness, fracture in upper or lower extremity, upper or lower extremity amputation, or Parkinson's disease;
- Physical activity (i.e., running, bicycling, etc.) ≥ 120 min/week;
- Use of anabolic medications (e.g. growth hormones or testosterone), anticholinesterase inhibitor (e.g. Aricept), or anticoagulant therapies (aspirin use is permitted);
- Dietary supplementation of grape seed extract or ginko biloba;
- Consumption of any dietary supplements containing resveratrol, quercetin, or *P. cuspidatum*;
- Use of other Investigational products;
- Dietary supplementation with CoQ10 or alpha-lipoic acid.

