Risks associated with resveratrol supplementation: Toxicity from the doses of resveratrol used in this study is likely to be low based on animal studies, and doses of 1000 mg/day have been well tolerated in previous safety trials in young and middle-age adults.[58-60] Additionally, a recent repeated-dosing study found that a dose of 200 mg of resveratrol at eight hour intervals for a three day period was well tolerated in older adults (age $\geq 65 \text{ years}$),[61] and doses of 1000 mg/day, 1500 mg/day, and 2000 mg/day of resveratrol supplementation were well tolerated in older adults during a four week intervention.[56] Based on the findings described above, we have chosen the test doses of resveratrol chosen for the proposed study to be 1000 mg/day and 1500 mg/day. Adverse effects of resveratrol have not been reported at these doses; however, long-term side effects are not known. Resveratrol is structurally similar to the synthetic estrogen diethylstilbestrol, and may have estrogenic activity. Resveratrol might also interact with blood thinners such as warfarin, and non-steroidal anti-inflammatory medications, thereby increasing the risk for bleeding. In our resveratrol pilot study, *The RIPE Trial*, resveratrol supplementation at 1000 mg/day had minimal effects on blood chemistries, and there were no significant differences in the number of participants reporting adverse or toxic events (e.g. headaches) across the three conditions (all p values > 0.05).

Risk management in participants using prohibited medication/interventions after study enrollment.

If the participant reports any change in medications, this information will be recorded in the participant's file (i.e., source documents and case report forms). If a participant reports use of any prohibited interventions as listed below and in sections 5.3.3. of the protocol (Prohibited Interventions) post-randomization, the participant will be withdrawn from the study.

Prohibited Interventions

• Active treatment for cancer, stroke, peripheral vascular disease, coronary artery disease, myocardial infarction, congestive heart failure (stage III or IV), valvular

heart disease, major psychiatric disease, severe anemia, liver or renal disease, diabetes, severe osteoarthritis, blindness or deafness, fracture in upper or lower extremity, upper or lower extremity amputation, or Parkinson's disease; - Safety Reasons

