- Hard Exercise (i.e., running, bicycling, etc.) ≥ 30 min/day on 5 or more days per week; *Scientific Reasons*
- Use of anabolic medications (e.g. growth hormones or testosterone), anticholinesterase inhibitor (e.g. Aricept), or anticoagulant therapies (aspirin use > 81 mg/day; aspirin use < 81 mg/day is permitted); -Safety Reasons
- Dietary supplementation of grape seed extract or ginko biloba; Scientific Reasons
- Consumption of any dietary supplements containing resveratrol, quercetin, or *P. cuspidatum; Scientific Reasons*
- Use of other Investigational products; Safety and Scientific Reasons
- Dietary supplementation with CoQ10 or alpha-lipoic acid. Scientific Reasons

If the participant reports changes in health, medications, or lifestyle other than the interventions listed above, the study physician will evaluate the safety of participants to continue in the intervention based on these reported changes. In these circumstances, the role of the study physician will be to provide recommendations to the study team regarding whether or not the participant should continue in the study based on reported changes in health, medication use, or lifestyle.

Adverse events will be graded according to Common Terminology Criteria for Adverse Events (CTCAE) v 4.03. In compliance with the Federal Registry, 21 CFR 312.32, effective April 1, 2008, we will use the following definitions for adverse event reporting:

Adverse event means any untoward medical occurrence associated with the use of a drug in humans, whether or not considered drug related.

Life-threatening adverse event or life-threatening suspected adverse reaction. An adverse event or suspected adverse reaction is considered "life-threatening" if, in the view of either the investigator or sponsor, its occurrence places the patient or subject at immediate risk of death. It does not include an adverse event or suspected adverse reaction that, had it occurred in a more severe form, might have caused death.

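### The on-study prohibited list appears in two conflicting versions (5.3.3 and 7.1), and the mandatory withdrawal rule cites both, so an eligible exerciser is due for withdrawal from day one

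*Combined protocol and SAP*

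**What the plan says.** Two sections carry an itemised list under the same title, and both are current text.

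- **Exercise.** Section 5.3.3 prohibits "Physical activity (i.e., running, bicycling, etc.) ≥ 120 min/week". Section 7.1 prohibits "Hard Exercise (i.e., running, bicycling, etc.) ≥ 30 min/day on 5 or more days per week". The entry criterion in 4.2 excludes "Hard exercise (i.e. running, bicycling, etc.) ≥ 30 min on five or more days per week", which is the 7.1 limit.
- **Aspirin.** Section 5.3.3 prohibits "anticholinesterase inhibitor (e.g. Aricept), or anticoagulant therapies (aspirin use is permitted"), with no dose attached. Section 7.1 has "anticoagulant therapies (aspirin use > 81 mg/day; aspirin use < 81 mg/day is permitted") and labels that item a safety reason. Section 4.2 has "anticoagulant therapies (note: aspirin -anti-platelet use (≤ 81 mg/day) is permitted"), and the biopsy paragraph of 7.1 repeats the limit of 81 mg or less.

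The consequence is set in 7.1, where the rule on reported use reads: "any prohibited interventions as listed below and in sections 5.3.3. of the protocol (Prohibited Interventions) post-randomization, the participant will be withdrawn from the study". Section 4.3 instead leaves continuation after prohibited use to the principal investigator and the study physician. Section 8 says that participants may be removed for non-compliance or medication use and, with permission, are followed after stopping study product. Section 9.4 lets treatment stop for the same kinds of reason while the participant stays on study. Sections 9.2 and 9.3 both aim for a second biopsy from everyone.

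Section 9.3 defines the per-protocol set partly by this test, "PP population will consist of individuals who did not take any prohibited therapies during the trial", and does not say which list it means.

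**The concern.** A rule that ends participation should rest on one list, and that list should agree with the entry criteria. Here the two versions err in opposite directions: 5.3.3 is stricter on exercise and 7.1 is stricter on aspirin. Following either section throughout therefore does not settle both items.

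The exercise item does the most damage. A participant can be properly enrolled, change nothing, and be in breach of 5.3.3 from the first dose. Because the withdrawal sentence in 7.1 names 5.3.3 as well as its own list, the plain instruction is to withdraw that person once the exercise is reported. The primary outcome comes from the second biopsy, so each withdrawn participant who does not return costs a primary observation.

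On aspirin, the two sections give staff opposite instructions about a dose above 81 mg/day. Section 7.1 treats that dose as a safety matter. The same section lists bleeding as a biopsy risk and warns of a possible interaction between resveratrol and blood thinners, and the second biopsy is still to come.

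**Working it through.** The plan gives no figure to reproduce. The check sets the limits side by side.

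**Exercise.** Inputs: 5.3.3, weekly total of 120 min or more; 7.1 and 4.2, at least 30 min on at least 5 days. The smallest weekly total that 7.1 can prohibit is 5 × 30 = 150 min. Every pattern barred by 7.1 is therefore barred by 5.3.3, but not the reverse.

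| Pattern | Min/week | Entry (4.2) | 5.3.3 | 7.1 |
|---|---|---|---|---|
| 2 × 60 | 120 | eligible | prohibited | allowed |
| 4 × 30 | 120 | eligible | prohibited | allowed |
| 5 × 25 | 125 | eligible | prohibited | allowed |
| 4 × 45 | 180 | eligible | prohibited | allowed |
| 4 × 90 | 360 | eligible | prohibited | allowed |
| 5 × 30 | 150 | excluded | prohibited | prohibited |

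The first five rows are people whom the trial admits on this criterion and whom 5.3.3 puts in breach. Section 7.1 sets no limit at four days or fewer.

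**Aspirin.**

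| Dose, mg/day | 4.2 | 5.3.3 | 7.1 list |
|---|---|---|---|
| 75 | permitted | permitted | permitted |
| 81 | permitted | permitted | neither prohibited nor expressly permitted |
| 100 | not permitted | permitted | prohibited |
| 325 | not permitted | permitted | prohibited |

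Doses above 81 mg/day are kept out at entry, so this conflict arises only when someone starts aspirin or raises the dose during the study.

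**What happens next.** For use of a listed item, 7.1 requires withdrawal and reserves physician review for changes not on the list. Sections 4.3, 8 and 9.4 make the outcome discretionary. The plan therefore also disagrees with itself on the consequence.

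**Scale.** Section 9.2 randomises 20 per arm and powers the trial on 18 completers, an allowance of 20 − 18 = 2 per arm. One withdrawn participant who does not return uses half of that allowance, and is 1/20 = 5.0% of the arm as randomised or 1/18 = 5.6% of the planned completers. These are the weights of a single case. The documents give no rates of exercise or aspirin use, so no expected number can be stated.

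**The case against.** The best defence is that 7.1 cites both lists and so means that either one triggers withdrawal. The stricter item would then apply each time: 120 min/week for exercise and 81 mg/day for aspirin. That is a possible reading, but it does not remove the problem. It withdraws the eligible cyclist, it overrides the express aspirin permission in 5.3.3, and 9.3 does not adopt it.

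The aspirin parenthesis in 5.3.3 may also be read as saying only that aspirin is not an anticoagulant, without ruling on dose. Even so, staff reading 5.3.3 alone would see nothing to act on.

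Three stronger readings are tempting, and the documents do not support them.

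- *A high-dose aspirin user would go to the second biopsy unreviewed.* Section 4.3 sends any medication change to the investigator and the study physician. That reduces the risk, though the two lists still give the reviewers opposite rules.
- *Exactly 81 mg/day is left undecided.* The list in 7.1 is loosely worded, but 4.2 and the biopsy paragraph of 7.1 both allow 81 mg or less.
- *The per-protocol results are at stake.* Section 9.2 specifies no per-protocol analysis. Section 9.3 speaks of therapies that a person takes, which covers aspirin directly but covers exercise only by interpretation.

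It also stands that Sections 8, 9.2 and 9.3 intend continued follow-up and a second biopsy. The withdrawal sentence in 7.1 does not say so.

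**Conclusion.** The point holds as an operational inconsistency with a possible cost in primary data, and is worth correcting. Two items conflict between the versions, and the exercise item in 5.3.3 also conflicts with entry. Under the mandatory rule in 7.1, an eligible participant doing, for example, 180 min/week over four days is to be withdrawn.

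The effect falls mainly on withdrawal, and through it on second biopsies. The per-protocol effect is secondary. The direct effect on the intent-to-treat definition is nil: that set requires both biopsies regardless of adherence and does not refer to the list. It shrinks only if a withdrawn participant does not come back.

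This rests on two assumptions: that staff apply the withdrawal sentence as written, and that the exercise or aspirin use is reported. How often either would happen cannot be estimated from the documents.

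**What to change.** 1. Keep one list, in 5.3.3, and have 7.1 and 9.3 cite it instead of repeating or implying it.
2. Exercise item: prohibit hard exercise of at least 30 minutes a day on at least five days a week, matching 4.2.
3. Aspirin item: prohibit more than 81 mg/day and permit 81 mg/day or less, also matching 4.2.
4. Bring the withdrawal sentence in 7.1 into line with 4.3, 8, 9.2, 9.3 and 9.4. Use of a listed item should lead to investigator and study-physician review of whether study product continues. The participant stays in follow-up and is still asked for the 90-day biopsy if the physician judges it safe.

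Leave the discretion in 4.3 as it stands. Narrowing it to unlisted changes would entrench mandatory withdrawal against 8 and 9.4, and could cost second biopsies.

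The cost is text edits to 5.3.3, 7.1 and 9.3. The diary and the medical-history update already collect concomitant interventions and medication changes; aspirin dose and exercise days and minutes need a line each. Dosing, visits, biopsies and the intent-to-treat definition do not change. The real concession is the 120 min/week cap: some participants may exercise more than 5.3.3 now allows. If the sponsor wants to keep that cap, the same limit has to go into 4.2.

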If all study entry criteria are met at the in-person screening visit, participants will be scheduled to return to the clinic for two baseline visits prior to randomization. During the first baseline visit, study staff will initially assess body mass and vital signs (e.g. pulse, blood pressure). Participants will then be asked to provide a fasting blood sample that will be utilized to evaluate clinical laboratory parameters. Following collection of the blood sample, participants will complete the following physical function tests: (1) the Short Physical Performance Battery (SPPB), (2) the Six Minute Walk Test, where participants will be asked to walk as far and fast as possible for 6-min on a 40 m track, and (3) isokinetic peak torque of the knee extensors and flexors of the dominant limb, unless contraindicated, will be assessed by dynamometer (Biodex Medical Systems, New York, NY) will be performed at this visit. Finally, the study coordinator will provide participants with a physical activity monitor. Participants will be asked to wear this monitor for a typical seven day period to objectively evaluate baseline physical activity habits. Also, during the Baseline Visit 1, study participants will be asked if they agree that left-overs of their tissue (muscle, blood) already collected for this study can be stored in the Tissue/Data Bank for future research. The Tissue/Data Bank has been approved by the UF IRB (IRB201300725, PI – [name], Department of Aging and Geriatric Research, University of Florida). The bank study has a separate consent form that needs to be signed by those who agree to participate in the bank.

Following this first baseline visit, participants will be invited to attend a second baseline visit to complete a muscle biopsy. Following completion of the Baseline Biopsy Visit, participants who satisfy all inclusion/exclusion criteria will be randomly assigned to receive resveratrol (1000 mg/day or 1500 mg/day) or placebo (vegetable cellulose). Participants will be provided with up to a 40-day supply of study drug capsules at the Baseline Biopsy Visit and will be asked to return to the clinic in approximately 30 days (± 7 days) for their 30-Day Visit.

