6.2.5 Completion/Final Evaluation

90-Day Visit. Study compound compliance will be assessed by means of capsule count by a study team member. Additionally, the following procedures will be performed:

- Contact and proxy contact information
- Vitals (blood pressure and heart rate)
- Body weight and girth measurement
- Blood draw for comprehensive metabolic profile (CMP), complete blood count (CBC w/diff), and inflammation markers
- Short Physical Performance Battery (SPPB)
- Six-Minute Walk Test
- Muscle endurance on the Biodex Machine
- Activity monitor will be dispensed to wear during 7-day period
- Adverse events will be collected; NCI Toxicity Criteria will be used to determine severity
- Product compliance

If the previous study visit (i.e. 60 day visit) is conducted outside of the allowable window, the target date for the 90-Day visit will be based on the date of the second baseline visit (BL2) which is when the participant started the study regimen.

• 90-Day Visit 2 (Muscle Biopsy). Participants will be scheduled for this appointment within 1 week of their 90-Day Visit. Muscle biopsies will be performed by [name]., who has performed numerous muscle biopsies for our previous studies, or other trained medical professionals if necessary. Skeletal muscle samples will be obtained under local anesthesia from the *vastus lateralis* muscle using a percutaneous needle biopsy technique as previously described by our group [62] (see **Appendix 1** for detailed description of procedure). The skin is closed with steristrips. Participants will be contacted by phone three days following this procedure, and will return for a wound check 10 days after the procedure date (see **Appendix 2** for detailed instructions and follow-up procedures for participants). Approximately 150-250 mg of muscle tissue is removed. Portions of the muscle will be immediately processed for permeabilized fiber high-resolution respiration measurements, and a very small piece of tissue will be mounted in embedding medium

and frozen in isopentane for future histochemical analysis. The remaining tissue will be immediately frozen in liquid nitrogen and stored at -80°C until analysis.

Follow-Up, 10 Day. After completion of the 90-Day Visit 2, participants will be scheduled to return to the clinic in approximately 10 days (\pm 3 days) for their Follow-Up 10 Day. The following tests will be performed:

- Contact information will be updated, if necessary

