Protection against risks associated with the six-minute walk test: Research staff who collect data have been trained in six-minute walk testing by other senior staff members with expertise in functional assessments, such as [name]. Re-certification is performed by a post-doctoral fellow (under [name] supervision) every six months. Study staff members are trained not to perform the six-minute walk test if they feel that testing is unsafe. In addition, participants are asked whether they feel the test is safe. Those who state it may be unsafe are not allowed to complete the test. During the testing sessions, a fully equipped defibrillator is available. All personnel associated with the study have received CPR training and training on management of acute events including syncope, chest pain, acute dyspnea, focal neurological symptoms, and abnormal vital signs. Portable defibrillators are available at the assessment site. Staff members are also trained to protect study participants against falling during testing. Additionally, a study physician is available on call, and contact numbers for emergency services are posted. Institutional and community EMS services will be activated if needed. If at any point during an assessment session, participants develop chest pain, shortness of breath, or dizziness, they will be instructed to rest, and to contact the center and their physicians if these symptoms persist or recur. In our experience conducting thousands of sixminute walk tests on individuals within various studies, the risk of falling is less than 1/500, and the risk of a fracture-associated fall is less than 1/2000. The risk of a significant cardiovascular event in association with the six-minute walk test is less than 1/3000.

Risks associated with SPPB measurement: Completion of the SPPB may be associated with the risk of falling, the development of chest discomfort due to coronary ischemia, or dyspnea due to heart failure or lung disease. Rarely, falling during the SPPB test may result in a fracture.

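### The per-protocol set is not tied to the outcome analysed: it can exclude an adherent participant with both biopsies because of a walk test withheld for safety (primary analysis unaffected; minor)

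*Combined protocol and SAP*

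**What the plan says.** Section 9.3 defines two populations that matter here.

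- **Intent-to-treat, primary outcome:** "Intent-to-treat population for the primary outcome is synonymous to those getting baseline and three-month biopsies, whether or not they adhere to the treatment". No other assessment is required.
- **Per protocol:** "The per protocol (PP) population will consist of all patients in the ITT population who are not major protocol violators". The next sentence makes this specific with three conditions: no prohibited therapies, at least 90% adherence by pill count, "and completed all baseline and post-treatment assessments". The last condition is not limited to the biopsies or to the outcome under analysis.

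The 90-day assessments in Section 6.2.5 include the SPPB, the "Six-Minute Walk Test", the Biodex test and a seven-day activity monitor. The same tests are listed for Baseline Visit 1 in Section 6.2.2.

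Section 7.1 says of the walk test: "Study staff members are trained not to perform the six-minute walk test if they feel that testing is unsafe". Of participants with doubts it says: "Those who state it may be unsafe are not allowed to complete the test".

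**The concern.** The two sentences of the per-protocol definition do not agree. The first excludes major violators. The second also excludes anyone with an incomplete battery, including a person whose walk test staff withheld as the protocol directs.

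For a per-protocol analysis of State 3, two things are at stake. Valid biopsy pairs from adherent participants would be discarded. If the omission occurs at day 90, the comparison would also be restricted to people judged fit for the function tests after treatment. Physical function is something the product is hypothesised to change (exploratory aims, Section 1.2). Section 2.1 reports that functional decline is strongly associated with reduced mitochondrial respiration. The selection is therefore on a post-randomisation variable that the plan itself connects to the outcome.

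**Working it through.** **Step 1. What the clause can exclude.** Per protocol is a subset of intent-to-treat. For the primary outcome, everyone in intent-to-treat has both biopsies. The completeness clause therefore adds nothing about biopsies, and for State 3 its only effect is to remove people who lack a non-biopsy assessment. It cannot be read as shorthand for having both biopsies.

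**Step 2. Whether the protocol itself creates such omissions.**

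| Assessment | Instruction to withhold? |
|---|---|
| Six-minute walk | Yes, explicit in Section 7.1, on the judgement of staff or participant |
| Biodex | Unclear. Section 4.3 has "isokinetic peak torque of the knee extensors and flexors of the dominant limb, unless contraindicated", which may concern only the choice of limb. The Biodex text in Section 7.1 gives precautions but no instruction to withhold |
| SPPB | None found |
| Activity monitor | None found. Section 6.2.2 asks for extra wear at baseline if fewer than 5 days were recorded |

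The walk test alone is enough for the point. A walk withheld at baseline precedes randomisation, so it costs biopsy pairs without post-randomisation selection. A walk withheld at day 90 does both.

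**Step 3. The plan's own power figure, for scale.** Section 9.2 gives 18 completers per arm, correlation 0.7, and 80% power at 0.69 SD for the contrast of the two active arms with placebo.

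- SD of change = √(2 × (1 − 0.7)) = 0.775 SD.
- SE of contrast = 0.775 × √(1/18 + 1/36) = 0.775 × 0.2887 = 0.224 SD.
- Power at 0.69 SD = 87.0% (normal) or 85.7% (t, 51 df).
- Detectable difference at 80% = 0.63 to 0.64 SD.

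The stated 80% is not reproduced exactly. It is conservative, and matches an SD of change of 0.837, a correlation of 1 − 0.837²/2 = 0.65. This has no bearing on the population definition. Both SDs are carried forward below.

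**Step 4. Illustration of loss.** The documents give no omission rate, so the loss fraction m is an assumption. The SE inflation is √(1/(1 − m)) − 1, whatever the starting n. The starting value of 18 per arm is also only illustrative.

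| Assumed m | 18 × (1 − m) | SE increase | n used | Power at 0.69 SD, correlation 0.7 | Power, calibrated to 80% at n = 18 |
|---|---|---|---|---|---|
| 0 | 18.0 | 0% | 18 | 85.7% | 80.0% |
| 5% | 17.1 | 2.6% | 17 | 83.6% | 77.6% |
| 10% | 16.2 | 5.4% | 16 | 81.2% | 75.0% |
| 20% | 14.4 | 11.8% | 14 | 75.6% | 69.0% |

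These figures cover precision only. Selection bias would be additional, and the documents give nothing from which to estimate it.

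**The case against.** The strongest reply is that nothing important uses this set. Section 9.3 calls intent-to-treat the lead principle ("The gold standard for clinical trials is by intent-to-treat"), and Sections 9.1 and 9.2 assign neither the primary contrast, the pairwise tests nor any sensitivity analysis to the per-protocol set. A completer analysis is promised in Sections 5.4 and 9.3 but is not tied to the per-protocol definition. This stands, and it limits the point to supportive analyses.

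Three stronger readings are tempting, and the documents do not support them.

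- A reader might infer that these participants drop out of the State 3 analysis as such. They do not: the primary population needs only the two biopsies.
- A reader might infer that staff are also told to withhold the Biodex. The wording in Section 4.3 is ambiguous, and only the walk test has an explicit instruction.
- A reader might take 18 per arm as a ceiling on the per-protocol set. It is a planning number of completers out of 20 randomised per arm. The per-protocol set has its own adherence and prohibited-therapy conditions, so its size is not stated.

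It is also fair to say that eligibility reduces the number affected. Section 4.1 requires willingness to undergo all testing, and Section 4.2 excludes SPPB below 4, severe osteoarthritis and recent fracture. The number need not be zero: an SPPB of 4 is admitted, and Section 3 seeks diverse functional status.

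Finally, any per-protocol set selects on post-randomisation behaviour, including the 90% adherence rule. That is true, but adherence is what a per-protocol analysis is meant to condition on. An unrelated function test is not.

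**Conclusion.** The point holds as a defect in the definition, of minor severity. As worded, Section 9.3 would classify a compliant, adherent participant with two biopsies as outside the per-protocol set because of a walk test withheld under Section 7.1. Any per-protocol analysis of State 3, or a completer analysis run on the same set, would lose valid pairs and be partly conditioned on day-90 function. The primary intent-to-treat result and the stated power are unchanged. The loss of precision, about 3% to 12% in the standard error, rests wholly on assumed omission rates of 5% to 20%. The conclusion itself rests only on reading the completeness clause literally. If the sponsor meant something narrower, the text should say so before unblinding, since membership would otherwise be settled after the data are seen.

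**What to change.** In Section 9.3, replace the completeness condition with: *has the baseline and post-treatment measurement of the outcome being analysed*. Specify that for State 3 and the other biopsy outcomes this means both biopsies. Add one sentence saying that an assessment withheld under the protocol's own safety provisions is not a protocol violation.

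The adherence and prohibited-therapy conditions stay as they are, and no stated sample-size or power figure changes. The cost is a short text edit. The one drawback is that the per-protocol n will differ between outcomes and must be shown in each table.
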